C _{max}	Maximum plasma concentration
CT	Computed tomography
CTCAE	Common Terminology Criteria for Adverse Events
CYP	Cytochrome P ₄₅₀
DDI	Drug-drug interaction
DNA	Deoxyribonucleic acid
DXA	Dual-energy x-ray absorptiometry scan
ECG	Electrocardiogram
ECOG	Eastern Cooperative Oncology Group
EOS	End of study
FACT-P	Functional assessment of cancer therapy-prostate
FDA	Food and Drug Administration
FPG	Fasting plasma glucose
FSH	Follicle stimulating hormone
GABA	Gamma-aminobutyric acid
GnRH	Gonadotropin releasing hormone
GCP	Good Clinical Practice
GLP	Good Laboratory Practices
HDL	High density lipoprotein
HIPAA	Health insurance portability and accountability act
HR	Hazard ratio

COMIRB/Protocol # 14-0909**Protocol Version:****4.27.2018 PI: [name]**

Abbreviation	Term
IB	Investigator's Brochure
ICF	Informed Consent Form
ICH	International Conference on Harmonisation
IEC	Independent Ethics Committee
IND	Investigational new drug
IRB	Institutional Review Board
IU	International units
LDL	Low density lipoprotein
LH	Leutinizing hormone
LHRH	Leutinizing hormone releasing hormone
MedDRA	Medical Dictionary for Regulatory Activities
MTD	Maximum tolerated dose
NCI	National Cancer Institute
NCI CTCAE	National Cancer Institute Common Terminology Criteria for Adverse
NYHA	New York Heart Association
PI	Principal investigator
PD	Progressive disease
PFS	Progression-free survival
PSA	Prostate specific antigen
PCWG2	Prostate Cancer Working Group 2
QOL	Quality of life
RECIST	Response Evaluation Criteria in Solid Tumors
SAE	Serious adverse event
SPPB	Short physical performance battery
SRE	Skeletal related event
SUSAR	Serious Unexpected Suspect Adverse Reaction
SHIM	Sexual Health Inventory in Men
T _{1/2}	Terminal half life
UCH-North	University of Colorado Health – Poudre Valley Hospital
ULN	Upper limit of the normal range
V/F	Volume of distribution
WHO	World Health Organization

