In the randomized clinical trial in patients with metastatic castration-resistant prostate cancer who had previously received docetaxel, 1200 patients were enrolled. The most common adverse drug reactions ($\geq 5\%$) reported in patients receiving enzalutamide in the randomized clinical trial were asthenia/fatigue, back pain, diarrhea, arthralgia, hot flush, peripheral edema, musculoskeletal pain, headache, upper respiratory infection, muscular weakness, dizziness, insomnia, lower respiratory infection, spinal cord compression and cauda equina syndrome, hematuria, paresthesia, anxiety, and hypertension ³³. Severe, grade ≥ 3 adverse events, were reported in 47% patients receiving enzalutamide and 53% of patients receiving placebo. The most common adverse reaction leading to treatment discontinuation in the enzalutamide treated group was seizure, which occurred in 0.9% of the enzalutamide-treated patients compared to none (0%) of the placebo-treated patients. In the Phase III trial, 7 of 800 patients treated with enzalutamide experienced a seizure in comparison to 0 events in the placebo arm. The seizures occurred days 31-603 after drug initiation. No further seizures occurred after patients discontinued enzalutamide. Patients were never readministered enzalutamide while on study, and patients with a history of seizure have been excluded in additional studies. It is thought that the mechanism of seizure may be the inhibition of the GABA-gated chloride channel. It is suggested that enzalutamide may lower the seizure threshold but not directly contribute to these events. This trial will exclude patients with a predisposition to seizure, as the exclusion of this subset of patients should not have a known impact on altering the incidence of metabolic syndrome. Another notable adverse event associated with the enzalutamide treatment arm is fall and fall-related injuries. This occurred in 4.6% of patients enrolled in the randomized trial and assigned to the enzalutamide treatment group in comparison to 1.3% of patients treated with placebo. The mechanism of fall is not clear. Fall-related injuries are described as joint injuries, non-pathologic fractures, and hematomas.

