12. ADVERSE EVENTS

12.1 Definitions

Definition of Adverse Events (AEs)

An adverse event (AE) is defined as any untoward medical occurrence in a subject administered a study drug and which does not necessarily have a causal relationship with this treatment. An AE can therefore be any unfavorable and unintended sign (including an abnormal laboratory finding), symptom, or disease temporally associated with the use of a study drug, whether or not related to the study drug.

An abnormality identified during a medical test (e.g., laboratory parameter, vital sign, ECG data, physical exam) should be defined as an AE only if the abnormality meets one of the following criteria:

- Induces clinical signs or symptoms.
- Requires active intervention.
- Requires interruption or discontinuation of study medication.
- The abnormality or investigational value is clinically significant in the opinion of the investigator.

All adverse events, whether or not related to the study drug, must be fully and completely documented.

Definition of Serious Adverse Events (SAEs)

An AE is considered "serious" if, in the view of either the investigator or sponsor, is unexpected and is potentially related to study participation and it results in any of the following outcomes:

- Results in death,
- Is life threatening (an AE is considered "life-threatening" if, in the view of either the investigator or sponsor, its occurrence places the subject at immediate risk of death. It does not include an AE that, had it occurred in a more severe form, might have caused death.),
- Results in persistent or significant disability/incapacity or substantial disruption of the ability to conduct normal life functions,
- Results in congenital anomaly, or birth defect,

- Requires inpatient hospitalization or leads to prolongation of hospitalization (hospitalization for treatment/observation/examination caused by AE is to be considered as serious),
- Other medically important events.

Serious Adverse Event Reporting

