For patients on enzalutamide therapy, within 48 hours of awareness of a serious adverse event, whether or not related to enzalutamide, the Investigator will complete and submit a Medwatch 3500A Form, containing all required information (reference 21 CFR 312.32). The Investigator will submit a copy of this MedWatch 3500A form to FDA and Astellas by either e-mail or fax, within the same timeframe if subject is on enzalutamide. If submission of this SAE to FDA or Astellas or is not possible within 48 hours, the Investigator's local drug safety contact (IRB, etc.) should be informed by phone.

The SAE documentation, including the Medwatch 3500A Form and available source records should be emailed or faxed to:

Astellas Pharma Global Development – United States
Email: [contact]
[contact]

The following minimum information is required:

- Study number/IIT regulatory identifier
- Subject number, sex and age
- The date of report
- A description of the SAE (event, seriousness of the event)
- Causal relationship to the study drug

Follow-up information for the event should be sent within promptly (within 7 days) as necessary.

All SAEs , regardless of treatment arm, will be reported to the University of Colorado DSMC within 48 hours of awareness of the event.

Procedure in Case of Pregnancy

The effect of enzalutamide in pregnant and lactating women is not known, and the exposure of a fetus or nursing infant is considered a potential risk. Enzalutamide can cause fetal harm when administered to a pregnant woman based on its mechanism of action. Subjects receiving enzalutamide are advised to use 2 acceptable methods of birth control (one of which must include a condom as a barrier method of contraception) starting at the time of screening for an enzalutamide study and continuing throughout the course of treatment and for at least three months after enzalutamide is discontinued.

If during the conduct of the clinical trial, a male subject impregnates his partner, the subject should report the pregnancy to the Investigator. The Investigator should report the pregnancy to the Sponsor as an SAE within 24 hours of awareness of the event. The expected date of delivery or expected date of the end of the pregnancy, last menstruation, estimated fertility date, pregnancy result and neonatal data etc., should be included in this information.

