12.3 Monitoring of Adverse Events and Period of Observation

AEs, both non-serious and serious (which include all deaths), will be monitored throughout the study as follows:

- AEs will be reported from the time of consent through 30 days after administration of the last dose of study drug and recorded.
- Serious pretreatment events will be reported to Astellas, Inc. from the time of the signing of the informed consent form (ICF) up to first dose of study drug.
- SAEs will be reported to Astellas, Inc. from the time of consent through 30 days after administration of the last dose of study drug and recorded. All SAEs should be monitored until they are resolved or are clearly determined to be due to a patient's stable or chronic

condition or intercurrent illness (es). If an SAE occurs in the follow-up period and is thought to be possibly related to study drug, it must be reported.

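### Section 12.1 makes an adverse event serious only if it is also unexpected and potentially related, which conflicts with section 12.3 and can keep known drug reactions out of 48-hour reporting and the SAE count

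*Combined protocol and SAP*

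**What the plan says.** Under the SAE heading in section 12.1, an event is serious if, in the view of the investigator or the sponsor, it "is unexpected and is potentially related to study participation and it results in any of the following outcomes". The listed outcomes include death, threat to life, lasting disability, birth defect, hospitalization and other medically important events. No other definition of a serious event appears in the protocol.

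Four other parts of the plan bear on that definition:

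- **Section 12.1, SAE reporting.** For enzalutamide patients, a report goes to the FDA and the drug supplier "within 48 hours of awareness of a serious adverse event, whether or not related to enzalutamide". One of the required report items is "Causal relationship to the study drug". SAEs in either arm also go to the DSMC within 48 hours.
- **Section 12.3** (numbered 12.4 in the table of contents). It opens: "AEs, both non-serious and serious (which include all deaths), will be monitored throughout the study as follows".
- **Section 11.** SAEs are one of the tabulated safety categories.
- **List of abbreviations.** SAE has its own entry, separate from SUSAR, which is spelled out as "Serious Unexpected Suspect Adverse Reaction".

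**The concern.** Seriousness describes what happened to the patient. Expectedness and relatedness are separate judgements. Section 12.1 merges all three, so an event with a grave outcome can fail the definition because it was foreseen or was put down to another cause.

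The word with most effect is the one requiring the event to be unexpected, because it removes the reactions already known for the drug. Section 1.5 describes several on enzalutamide: "In the Phase III trial, 7 of 800 patients treated with enzalutamide experienced a seizure"; for falls and fall-related injuries, "This occurred in 4.6% of patients enrolled in the randomized trial and assigned to the enzalutamide treatment group"; and the list of common reactions includes "spinal cord compression and cauda equina syndrome". If these count as expected, such an event with a listed outcome is not an SAE under 12.1, even when judged drug-related.

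At stake are the classification itself, the 48-hour reports to the FDA and the supplier (enzalutamide patients) and to the DSMC (both arms), and the SAE row in section 11. Safety is a secondary endpoint (section 3.2). What counts as expected can differ between enzalutamide and ADT, so SAE counts may also be hard to compare between arms.

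**Working it through.** The plan gives no SAE rate, so there is no figure of its own to reproduce. The main check is a comparison of texts.

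**Step 1: how the conditions combine.** Section 12.1 joins three conditions with the word *and*: unexpected, potentially related to study participation, and a listed outcome. All three must hold.

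**Step 2: test cases.**

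| Event | Under 12.1 | Under other text |
|---|---|---|
| Death from the underlying cancer, judged unrelated | Not serious | Serious under 12.3 |
| Death from a known drug reaction | Not serious (expected) | Serious under 12.3 |
| Drug-related seizure with hospitalization, treated as expected because section 1.5 describes it | Not serious | 12.3 does not help, as it names only deaths |
| Hospitalization judged unrelated to study participation | Not serious | Fits poorly with 48-hour reporting regardless of relatedness to enzalutamide |

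Rows 1 and 2 contradict 12.3 on its natural reading. Row 4 is supporting evidence only: 12.1 speaks of study participation, which is wider than enzalutamide, so an event unrelated to the drug could still be related to participation.

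**Step 3: what depends on the definition.** Both 48-hour routes in 12.1 and the SAE category in section 11 apply only to events classed as SAEs. An event that fails the definition reaches neither. No other SAE rule in the protocol uses expectedness, and 12.1 names no reference against which to judge it.

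**Step 4: illustration of size, for the unexpectedness condition only.** Inputs: 28 patients per arm (section 10.1); seizure in 7 of 800 and falls or fall-related injuries in 4.6% on enzalutamide (section 1.5). Assumption: those rates apply here.

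Expected patients = n × p; chance of at least one = 1 − (1 − p)^n.

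- Seizure: p = 7/800 = 0.00875. Expected: 28 × 0.00875 = 0.245. Chance of at least one: 1 − (0.99125)^28 = 0.218.
- Falls: p = 0.046. Expected: 28 × 0.046 = 1.288. Chance of at least one: 1 − (0.954)^28 = 0.732.

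These are chances of any such event, not of a misclassified one. The share with a listed outcome is not given, so it is taken as 0 to 100%. The number that could be misclassified is then 0 to 0.245 patients for seizure and 0 to 1.288 for falls.

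**The case against.** Several points can be made for the plan:

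- **The text says *if*, not *only if*.** True, but it is the sole definition, so a site has to apply it as the test.
- **The remark about deaths in 12.3 is a parenthesis.** It could describe all monitored events, which would remove the contradiction. The likelier reading attaches it to serious events.
- **The hospitalization item in 12.1 carries its own statement that hospitalization caused by an adverse event is serious.** It still stands under the conditional opening. At best it adds to the inconsistency.
- **Relatedness may matter little in practice.** The reporting rules, and the follow-up of SAEs until they resolve or are attributed to another illness, presuppose that unrelated events can be SAEs. This is fair, and it leaves unexpectedness as the main gap.
- **Section 11 introduces its tables as treatment-related events.** Read just as literally, that would drop unrelated SAEs whatever 12.1 says. This stands, and the fix has to cover it. The table of grade 3 or higher events sits under the same lead-in, so it is a weaker safeguard than it looks.
- **The SUSAR entry shows nothing about how 12.1 was drafted.** Agreed. It shows only that the protocol lists the two terms separately and that the conditions in 12.1 resemble the narrower one.
- **The events are not lost.** Section 12.1 requires every adverse event to be documented. Section 11 lists events leading to discontinuation. Section 11.1 provides working-group review and a six-month report to the DSMC. Section 12.2 has the investigator supply all adverse events, serious or not, at the end of treatment and of follow-up. This limits the harm, but none of it restores the 48-hour clock or the classification.

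**Conclusion.** The concern holds. As written, 12.1 ties seriousness to expectedness and relatedness. That contradicts 12.3 for deaths and fits poorly with the reporting rules in 12.1 itself. Confidence in this is high, because it rests on the wording and not on the event rates.

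The practical size is uncertain. There is no SAE rate for this trial and no reference for expectedness, so the total under-count cannot be estimated. How late the DSMC would hear depends on which adverse events section 11.1 treats as reportable, and the documents do not define that. The illustration gives at most about 0.25 seizure patients and 1.3 fall patients, with a lower bound of zero in each case. Its rates come from castration-resistant patients previously given docetaxel, and those seizures occurred as late as day 603, against 12 months of treatment here. This trial also excludes men predisposed to seizure, so the true figures may be lower.

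This should be fixed: expedited reporting and the SAE count are exposed, while the primary endpoint is not.

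**What to change.** 1. In the SAE definition in 12.1, delete the words that require the event to be unexpected and potentially related to study participation, so that a listed outcome alone makes an event serious. This brings the definition into line with 12.3 and with the reporting rules in 12.1.
2. Record expectedness and relatedness as separate fields for each SAE, and name the reference for expectedness.
3. In section 11, state that the SAE row counts all SAEs regardless of relatedness. Without this, the treatment-related lead-in could still exclude some.
4. The same amendment could settle a separate inconsistency: the deadline for SAE reports to the DSMC is 48 hours in 12.1 and 5 business days in 11.1.

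The cost is a one-line change to 12.1, short clarifications elsewhere, IRB approval of the amendment (section 13.6), and somewhat more SAE paperwork. No visits or procedures are added.

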12.2 Maintenance of Safety Information

Safety information will be maintained in a clinical database/repository in a retrievable format. At a minimum, at the end of the treatment phase (="last patient off treatment") as well as the end of the follow-up phase (="last patient out") of the Study, the Principal Investigator shall provide all adverse events, both serious and non-serious, in report format. However, in certain circumstances more frequent review of the safety data may be necessary, e/g/ to fulfill a regulatory request, and as such the data shall be made available within a reasonable timeframe at Astellas, Inc.'s request.

12.2.1 Product Quality Complaints

Any product quality complaint, with or without an AE, (including reports of suspicion of counterfeiting, diversion, or tampering, and suspected transmission of pathogens) will be transmitted by the Principal Investigator within **24 hours** of becoming aware of the event(s).

12.3 Monitoring of Adverse Events and Period of Observation

AEs, both non-serious and serious (which include all deaths), will be monitored throughout the study as follows:

- AEs will be reported from the time of consent through 30 days after administration of the last dose of study drug and recorded.
- Serious pretreatment events will be reported to Astellas, Inc. from the time of the signing of the informed consent form (ICF) up to first dose of study drug.
- SAEs will be reported to Astellas, Inc. from the time of consent through 30 days after administration of the last dose of study drug and recorded. All SAEs should be monitored until they are resolved or are clearly determined to be due to a patient's stable or chronic

condition or intercurrent illness (es). If an SAE occurs in the follow-up period and is thought to be possibly related to study drug, it must be reported.

13. ADMINISTRATIVE REQUIREMENTS

This is an investigator-initiated trial and thus major trial decisions and document design will occur with the PI and supporting institution, the University of Colorado Cancer Center. Astellas Inc. is providing study support and thus will have access to trial data and patient safety information.

13.1 Data Quality Assurance

The investigator is required to prepare and maintain adequate and accurate case histories designed to record all observations and other data pertinent to the study for each study patient. Study monitors will discuss instances of missing or uninterpretable data with the investigator for resolution. Any changes to study data will be monitored via an audit trail.

13.2 Study Monitoring

Monitoring for this study will be performed by CU Cancer Center Clinical Monitor in accordance with the clinical monitoring plan (CMP), incorporated herein by reference. The CMP describes in detail who will conduct the monitoring, at what frequency monitoring will be done, at what level of detail monitoring will be performed, and the distribution of the monitoring reports.

The CMP will be approved by the PI and will be followed to comply with GCP guidelines. All study records must be consistent with the patient's source documentation. During the course of the study, the study monitor will make study site visits to review protocol compliance, verify study record against source documentation, assess drug accountability, and ensure that the study is being conducted according to pertinent regulatory requirements. The review of medical records will be performed in a manner that ensures that patient confidentiality is maintained.

Independent audits will be conducted by the CU Cancer Center DSMC to ensure monitoring practices are performed consistently across all participating sites, if applicable, and that monitors are following the CMP.

13.3 Ethical Considerations

The study will be conducted in accordance with applicable regulatory requirement(s) and will adhere to GCP standards. The IRB/IEC will review all appropriate study documentation to safeguard the rights, safety, and well-being of the patients. The protocol, Investigator Brochure (IB), ICF, advertisements (if applicable), written information given to the patients (including diary cards), safety updates, annual progress reports, and any revisions to these documents will be provided to the IRB/IEC by the investigator, as allowed by local regulations.

13.4 Patient Information and Informed Consent

After the study has been fully explained, written informed consent will be obtained from either the patient or his/her guardian or legal representative before study participation. The method of obtaining and documenting the informed consent and the contents of the consent must comply with the ICH-GCP and all applicable regulatory requirements.

13.5 Patient Confidentiality

To maintain patient privacy, study drug accountability records, study reports, and communications will identify the patient by initials where permitted and/or by the assigned patient number. The patient's confidentiality will be maintained and will not be made publicly available to the extent permitted by the applicable laws and regulations.

13.6 Investigator Compliance

Changes to the protocol will require written IRB/IEC approval/favorable opinion before implementation, except when the modification is needed to eliminate an immediate hazard or hazards to patients. When immediate deviation from the protocol is required to eliminate an immediate hazard or hazards to patients, the investigator will contact Astellas, Inc., or a designee, if circumstances permit, to discuss the planned course of action. Any departures from the protocol must be documented.

13.7 On-site Audits

Regulatory authorities, the IRB, and/or Astellas, Inc. may request access to all source documents, and any study documentation for on-site audit or inspection. Direct access to these documents must be guaranteed by the investigator, who must provide support at all times for these activities.

